Individuals will then initiate treatment on all lesions of LP BID and will be evaluated weekly and assessed by PGA, BSA, lesion count; Modified CAILS, Pruritus NRS, and Skindex-16 between weeks 0-4 (see Appendix). Week 4 will be the primary endpoint; however therapy will be continued for an additional 4 weeks. Therapy will be stopped and the individuals will be evaluated at week 8 and assessed by PGA, BSA, lesion count, Modified CAILS, Pruritus NRS, and Skindex-16. Laboratory and safety monitoring will occur at weeks 1, 2, 3, 4, and 8, and 12. 3D Photographs will be taken at weeks 0, 1, 2, 3, 4, 8, and 12. Individual lesions will be circled at that time and the exact volume of each lesion will be measured. Up close photos will be taken of the disease and normal tissues attained at weeks 0 & 4.

Tissue will be collected for RNA sequencing at week 0 and 4. Blood collection will include the isolation at week 0, 2, and week 4, 5mL vials of blood which will be separated and the serum and cell pellet will be stored for future analysis. Five skin biopsies will be taken during the study. At week 0, up to two 3mm tissue biopsies will be taken from lesional skin and one biopsy will be taken from normal appearing skin. The initial biopsy of lesional tissue and control will be

annotated. At week 4, up to two 3mm biopsies will be taken from lesional responsive tissue and lesional refractory tissue. Responsive and non-responsive lesions will be determined by the change in Modified CAILS between week 0 and 4. Responsive will require a 50% reduction in Modified CAILS and non-responsive can have progression, no change, or up to a 50% reduction in Modified CAILS. The lesions will be chosen using full body photographs taken at week 0. Up to 60 samples will be snap frozen and stored in the tissue biobank. Once completed, RNA sequencing will be performed on the 60 tissue samples and analysis will be performed. Paired analysis of treatment responsive and refractory lesions will be made as well as treated and untreated lesions.

Nucleic Acid Extractions: RNA will be extracted from a total of 50 um of fresh tissue using the Qiagen FFPE RNeasy Micro extraction Kit according to manufacturer's recommendation.

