4.2 Number of Subjects

12 subjects will be enrolled in this study.

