8.1 Sample Size Determination

Data analysis: Assuming a medium effect size (0.3) and a target power of 80%, a two-armed study would need about 108 subjects and a single arm about 88 subjects. Due to the costs associated with a study, we propose a single armed study of 12 subjects with corollary science including RNA sequencing. This will reduce costs and provide biomarkers predictive of response. Effect sizes will be estimated for the appropriate statistical tests that will be used for group comparisons in future studies. This will enable more accurate power and sample size estimates moving forward.

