8.2 Statistical Methods

Descriptive Statistics

Sample Size Computation and Power Analysis:

The sample size for this pilot study is set at 12 subjects for logistical and financial reasons. This is similar in size to other exploratory studies and will provide adequate data for estimation purposes for planning future studies. With 12 subjects, the study is intended to be for estimation purposes only.

Statistical Analysis Plan:

Data Analysis - The statistical analysis will provide descriptive summary statistics for categorical and continuous outcomes. Categorical variables will be described by their count and proportion of occurrence while continuous, normally distributed variables will be described by their mean and standard deviation; and continuous, non-normally distributed variables will be described by their median and range. The paired or unpaired Wilcoxon tests will be used to quantify differences in numerical outcomes while the Fisher's exact test and the McNemar's or Bowker's tests will be used to quantify changes in categorical variables.

If missingness occurs at random a mixed model will be utilized to assess the change in the lesion over time. A sensitivity analysis will be performed using the last observation carried forward and the results will be compared to that of the mixed-model.

Effect sizes will be estimated for the appropriate statistical tests that will be used for group comparisons in future studies. This will enable more accurate power and sample size estimates moving forward.

Bioinformatic Analysis:

RNA-seq analysis: We will use our recently developed LinNorm program (<https://www.bioconductor.org/packages/release/bioc/html/Linnorm.html>) to process RNA-seq data and detect differentially expressed genes (DEGs) by comparing the RNA-seq profiles. We will first find DEG between responsive and non-responsive samples from the same individual by using paired or unpaired Wilcoxon rank-sum test (depending on how the samples are collected). We will then rank each gene in the DEGs based on the occurrence frequencies in all 12 subjects

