to find common DEGs for responsiveness (use permutation test to determine the p value). For the top ranked genes (common DEGs), we will use DAVID (3) and GSEA (4) software to find enriched inflammatory pathways and GO terms for the DEGs. By comparing the normal tissue with the pathogenic tissue (responsive + non-responsive) using the above approach, we will detect a common DEGs for LP pathogenesis. Hierarchical clustering (5) and Principal Component Analysis (PCA) (6) will be applied to samples for their hierarchical relationship and clustering properties. Ideally normal, responsive and non-responsive tissues should form three distinct groups. The PCA analysis will provide us a set of gene signatures that can distinguish these three types of tissues. The common DEGs for responsiveness and pathogenesis, as well as gene signature from PCA will be used for our pathogenesis or survival prediction. We will perform structure variants calling from RNA-seq data with SNPiR (7), and reconstruct gene co-expression networks with ARACHNE.(8) Additionally, we will perform de-convolutional analysis, to compare the immune profiles of responsive and non-responsive tissue and to correlate immune profiles. Predictive biomarkers will be correlated with lesional and global responses.

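### Section 8.2 gives GSEA only the common-DEG list instead of the ranking of all measured genes, so a modest coordinated pathway shift can be missed

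*Combined protocol and SAP*

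**What the plan says.** The bioinformatic part of section 8.2 sets out a chain of steps.

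- DEG calls are made subject by subject: "We will first find DEG between responsive and non-responsive samples from the same individual by using paired or unpaired Wilcoxon rank-sum test".
- Only genes already called are ranked: "We will then rank each gene in the DEGs based on the occurrence frequencies in all 12 subjects".
- The common ones are then picked out, "to find common DEGs for responsiveness (use permutation test to determine the p value"). No threshold, list length or multiplicity rule is given.
- That list goes to both pathway tools: "For the top ranked genes (common DEGs), we will use DAVID (3) and GSEA (4) software to find enriched inflammatory pathways and GO terms".
- The chain is reused for lichen planus pathogenesis: "By comparing the normal tissue with the pathogenic tissue (responsive + non-responsive) using the above approach".

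The text does not contain the word 'only', but no section gives GSEA a full gene ranking or an expression matrix. Clustering, PCA, variant calling, co-expression networks and deconvolution are also planned. None of them is a ranked gene-set test.

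On the tissue available, section 4.1 says "At week 4, up to two 3mm biopsies will be taken from lesional responsive tissue and lesional refractory tissue", and section 4.2 says "12 subjects will be enrolled in this study".

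**The concern.** DAVID-type over-representation needs a gene list. GSEA does not. Its running sum asks whether the genes of a pathway lie towards one end of the ranking of everything measured, and the title of the GSEA paper that the plan cites (reference 4) places the method at genome-wide profiles. On a pre-selected list most pathway genes are absent, and those that remain are compared only with other selected genes. That is a different question, and usually a weaker one.

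The pathway step is how the trial would show which inflammatory pathways go with response, which is part of its exploratory pharmacodynamic objective (section 3). Section 8.1 also offers the RNA sequencing as part of the reason for a 12-subject single-arm study. With at most 12 pairs, few single genes can be called reliably, so a small shift shared across a pathway is a plausible form for a real signal. A modest interferon/JAK effect, the mechanistic premise of section 2.1, could then be reported as not enriched.

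**Working it through.** **Number of pairs.** Section 4.1 allows up to three biopsies at week 0 and up to two at week 4. 12 × (3 + 2) = 60, which matches the 60 samples stated there. So there is at most one responsive/refractory pair per subject, and at most 12 pairs.

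**The plan's own figures.** None concerns the pathway analysis. The only power figures are the 88 and 108 subjects of section 8.1. With two-sided alpha 0.05 assumed, both reproduce as chi-square tests with w = 0.3: on 1 df, (1.960 + 0.842)² / 0.3² = 7.85 / 0.09 = 87.2, so 88; on 2 df, noncentrality 9.635 / 0.09 = 107.05, so 108. A comparison of two means at 0.3 SD would need 175 per arm. The 0.3 is therefore a clinical sample-size effect, and the expression shift below is an assumption.

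**Why the cut matters.** Let each gene have 12 within-subject differences, shift δ (in SD of the difference) and within-pathway correlation ρ.

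- Single gene: expected t is about δ√12, which is 0.69 at δ = 0.2 and 1.04 at δ = 0.3. Few such genes reach a short list.
- Mean of a 50-gene pathway at ρ = 0.05: variance (1 + 49 × 0.05) / 50 = 0.069, SD 0.263. The signal is 0.69 / 0.263 = 2.6 to 1.04 / 0.263 = 4.0 standard errors.
- At ρ = 0.2: variance (1 + 49 × 0.2) / 50 = 0.216, SD 0.465. At δ = 0.3 the signal is only 1.04 / 0.465 = 2.2 standard errors, so the full ranking also loses its edge.

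**Simulation, main setting.** 12 pairs, 50-gene pathway, 200-gene list, ρ = 0.05, one pathway tested at 5%. The GSEA statistic is the maximum deviation of [cumulative |t| of pathway genes / their total] − [cumulative count of other genes / their total]. Cut-list GSEA is calibrated by gene labels. Run 1 used 8,000 genes and 80 replicates (Monte Carlo SE up to about 6 points).

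| Shift | Run | GSEA, full ranking | GSEA, cut list | DAVID-type count |
|---|---|---|---|---|
| 0.2 SD | 1 | 63% | 23% | not run |
| 0.2 SD | 2 | 55% | 33% | 25% |
| 0.3 SD | 1 | 88% | 41% | not run |
| 0.3 SD | 2 | 85% | 48% | 60% |

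In run 1 an average of 2.9 (0.2 SD) and 4.5 (0.3 SD) of the 50 pathway genes survived the cut. Chance alone would leave 200 × 50 / 8,000 = 1.25.

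**A setting closer to the plan's selection rule.** Genes were selected by occurrence frequency across 12 subjects: 8,000 genes, 80-gene pathway, 300-gene list, ρ 0.05 to 0.10, 100 replicates (SE at most 5 points), all tests calibrated by sign flips.

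| Shift | Full ranking | Cut-list GSEA | Count |
|---|---|---|---|
| 0.2 SD | 54-73% | 22-31% | 18-24% |
| 0.3 SD | 74-93% | 18-33% | 37-38% |

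Sign flips are unkind to a cut list: its power hardly moves between 0.2 and 0.3 SD. I treat that column as supporting only. At zero shift the full ranking rejected in 1-7% of replicates, here and with 300 other changed genes added.

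**Where the gap closes.**

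- Longer list: at 0.3 SD with an 800-gene list, 94% (full) against 88% (cut). With 15,000 independent genes, a 100-gene pathway and a 500-gene list, 100% against 88% at 0.3 SD (count 73%), and 100% for both at 0.4 SD (count 97%).
- Higher correlation: at ρ = 0.2 and 0.3 SD, 44% against 31%, with the count at 28-30%.
- Large shift: at 0.6 SD, full ranking 93-100%, count 90-100%, gene-label cut-list GSEA 95-100%.

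Gene-label GSEA on a cut list looks strong in such settings partly because it rejects too often when genes are correlated, in up to about 20% of replicates at zero shift.

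**Upstream step.** With one responsive and one refractory sample, the smallest two-sided rank-sum p within a subject is 2/2 = 1.0. Two against two gives 2/6 = 0.33. The list handed to both tools may therefore be empty or arbitrary, and the simulations, which assume a workable list, are lenient to the plan.

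**The case against.** The strongest reply is that the plan does not rely on GSEA alone. DAVID runs on the same list, and a list-based count recovers part of the loss: at 0.3 SD in run 2 it reaches 60% against 85% for the full ranking, and at 0.6 SD it loses almost nothing. This stands. A reader might infer that most of the power of the pathway step is lost. The documents do not support that: they plan both tools, and they fix neither a list length nor an effect size.

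A reader might also take "Assuming a medium effect size (0.3) and a target power of 80" per cent as the plan's own expression effect in SD units. It belongs to the clinical sample size in section 8.1, and the plan states no gene-expression effect at all.

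Third, the list length in the simulations is assumed, and a long list removes most of the difference. This stands too, and it is why the result is a range tied to its assumptions.

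Fourth, other transcriptomic analyses are planned, the objective is exploratory, and section 8.2 describes the study as being for estimation. That limits the consequences. It does not justify giving GSEA a cut input, because none of the other analyses tests gene sets on a full ranking.

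Finally, the remedy needs an across-subject statistic that the plan does not define. It also needs a pooling rule where two pathogenic samples face one normal sample. Both objections are right, and the fix below supplies them.

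**Conclusion.** The point holds for modest shifts and short lists. As written, GSEA receives a selected list, and this can miss a coordinated pathway effect that the same samples and software could detect. With 12 pairs, a 50-gene pathway, a 200-gene list, a shift of 0.2 to 0.3 SD and correlation 0.05, power is about 55-90% on the full ranking, about 20-50% for GSEA on the cut list and about 25-60% for a DAVID-type count. All of these inputs except the 12 subjects are assumptions, and 12 complete pairs is the maximum.

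The advantage over the count is small or absent at 0.6 SD, and it narrows with long lists or high within-pathway correlation. It would be wrong to infer that a strong pathway effect would be missed: very low cut-list power at large shifts appears only when the cut list is calibrated by sign flips, and is an artefact of that calibration.

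This is a worthwhile correction to an exploratory analysis. The primary endpoint is unaffected.

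**What to change.** Replace the pathway sentence in section 8.2 with:

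> GSEA will be run on all expressed genes, ranked by a signed across-subject paired statistic (responsive minus non-responsive within subject), with no significance or top-rank cut. Significance will be assessed by within-subject sign-flip permutation, with FDR control across gene sets. DAVID over-representation of the common-DEG list, with the expressed genes as background, will be supportive.

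For the pathogenesis contrast, first average each subject's pathogenic samples, so that there is one pathogenic-minus-normal difference per subject. Then apply the same method.

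The cost is a little more analysis work to define and compute the across-subject statistic. Samples, sequencing and software stay the same.

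Two limits should be stated in the plan. The smallest two-sided sign-flip p is 2/2ⁿ, which is 2/4,096 = 0.00049 with 12 complete pairs and 2/256 = 0.0078 with 8, so incomplete pairs restrict what FDR control can deliver. And the DAVID list would still rest on the within-subject Wilcoxon calls, which this change does not repair.

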 12.2 CONFLICT OF INTEREST **ERROR! BOOKMARK NOT DEFINED.**

 12.3 SUBJECT STIPENDS OR PAYMENTS 25

13 PUBLICATION PLAN 25

14 REFERENCES 26

15 ATTACHMENTS 27

List of Abbreviations**LIST OF ABBREVIATIONS**

AE	Adverse Event/Adverse Experience
BSA	Body Surface Area
CAILS	Clinical Assessment Scale of Severity for Index Lesion Signs & Symptoms
CFR	Code of Federal Regulations
CRF	Case Report Form
CXCR3	Chemokine Receptor-3
CXCL9	Chemokines Ligands 9
DEGs	Differentially Expressed Genes
DSMB	Data and Safety Monitoring Board
FDA	Food and Drug Administration
GCP	Good Clinical Practice
GVHD	Graft Versus Host Disease
HIPAA	Health Insurance Portability and Accountability Act
IB	Investigator's Brochure
IL-1	Interleukin-1
IND	Investigational New Drug Application
IFN α	Interferon Alpha
IFN γ	Interferon Gamma
IRB	Institutional Review Board
JAK	Janus Kinase
LP	Lichen Planus
LTR	Lichenoid Tissue Reaction
MDC	Myeloid Dendritic Cells
NRS	Numerical Rating Scale
PDC	Plasmacytoid Dendritic Cells
PGA	Physician Global Assessment
PHI	Protected Health Information
PI	Principal Investigator
SAE	Serious Adverse Event/Serious Adverse Experience
SOP	Standard Operating Procedure

Study Summary

Title	INCB018424 PHOSPHATE CREAM in the Treatment of Cutaneous Lichen Planus
Running Title	INCB018424 PHOSPHATE CREAM in LP
Protocol Number	17-005406
Phase	Phase II
Methodology	Open-Label, Single Arm
Overall Study Duration	13 to 16 weeks
Subject Participation Duration	12 weeks
Single or Multi-Site	Single Site
Objectives	To evaluate the safety and efficacy of INCB018424 PHOSPHATE CREAM in cutaneous LP as assessed by the change in Physician Global Assessment (PGA), Body Surface Area (BSA), Index Treatment and Control Lesion by Modified Clinical Assessment Scale of Severity for Index Lesion Signs and Symptoms (Modified CAISL) score, Pruritus Numerical Rating Scale (NRS), and Skindex-16. To predict responses through the identification of unique biomarkers of LP at week 0 and utilizing RNA sequencing on responsive and non-responsive tissue at week 4.
Number of Subjects	12
Diagnosis and Main Inclusion Criteria	Non-pregnant adults with cutaneous LP involving less than 20% of the body surface area (BSA)
Study Product, Dose, Route, Regimen	INCB018424 PHOSPHATE CREAM 1.5%, topical application, twice daily on lesions of cutaneous LP.
Duration of Administration	Drug will be administered from Day 0 through Week 8.

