To determine the efficacy of INCB018424 PHOSPHATE CREAM and the duration of response after discontinuation as measured by the change in Pruritus NRS, (week 0 to week 4, week 0 to week 8, weeks 4 to 8, weeks 8 to 12), Change in Skindex-16 (week 0 to week 4, weeks 4 to 8, weeks 8 to 12), Change in Physician Global Assessment (PGA) (week 0 to week 4, week 0 to week 8, weeks 4 to 8, weeks 8 to 12), Change in BSA (week 0 to week 4, week 0 to week 8, weeks 4 to 8, weeks 8 to 12), Change in Modified CAILS (week 0 to week 8, weeks 4 to 8, weeks 8 to 12).

Exploratory Objectives:

To predict responses and examine the pharmacodynamics of treatment through the identification of unique biomarkers and transcriptomic changes of LP at week 0 and utilizing RNA sequencing on responsive and non-responsive tissue at week 4 To correlate these biomarkers with measures of global response: Modified CAILS, PGA, BSA, and lesion count.

4 Study Design

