4.1 General Description

This is a single center, exploratory, open-label, single-arm design study of 12 patients. Treatment naïve and treatment refractory patients with LP will be treated with INCB018424 PHOSPHATE CREAM. Patients who are non-responders, to physician choice standard of care, will undergo a washout period and will be enrolled in the study.

Multiple safety studies have been conducted with INCB018424 PHOSPHATE CREAM (see Safety) and a dose of 1.5% cream BID on up to 20% BSA is deemed safe. (Investigator's Brochure) The Within each cohort, the maximum reduction from baseline in the total psoriasis lesion assessment scores for the treated lesions was observed at the end of treatment (Day 28). (Investigator's Brochure) Therefore, we propose a single center, exploratory, open-label, single-arm design study of 12 patients. Treatment naïve and treatment refractory patients with LP will be treated with INCB018424 PHOSPHATE CREAM.

Individuals with LP involving less than 20% of the BSA will be eligible. Individuals must have 4 lesions at baseline, however, a minimum of 10 lesions is ideal, which are at least 5mm in diameter. 10 lesions are ideal as 2 lesions will be index lesions and 8 or more lesions will be selected from as responsive or non-responsive at 4 weeks. All lesions except for one index lesion will be treated and all lesions will be annotated, photographed, and scored. The rationale for a minimum of 8 lesions is based upon the assumption of a 50% response rate at 2 weeks. With 8 lesions, there would be a less than 1% chance that all 8 lesions would respond. Ideally, the 2 index lesions will be 10mm in diameter but this is not a requirement. Prior treatment will be allowed; however, a washout period of 2 weeks for topical and 4 weeks for systemic agents is required. At the washout period, individuals will undergo evaluation with a PGA, BSA calculation, and have the 2 largest, representative lesions selected for evaluation using a modified CAILS score lesion A- treatment index lesion and B-index control lesion. The determination of which lesion receives treatment and which is a control will be determined randomly. The additional lesions will be photographed, measured, scored, and recorded with Modified CAILS scores as well. The later calculations will be used for the determination of responsive and non-responsive lesions. Additional Pruritus measures using the NRS and Skindex-16 will be collected at that time.

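### On its natural reading, the Section 8.2 pathogenesis contrast sets week-0 normal skin against week-4 treated lesions, and its within-subject first step cannot flag any gene

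*Combined protocol and SAP*

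**What the plan says.** Section 8.2 (Bioinformatic Analysis) plans two differential-expression contrasts. The first compares responsive with non-responsive samples within each individual by a paired or unpaired Wilcoxon test, then ranks genes by how often they are selected across the 12 subjects, with a permutation p value. The second reuses that procedure to find genes for LP pathogenesis: "By comparing the normal tissue with the pathogenic tissue (responsive + non-responsive) using the above approach". Neither contrast has a stated visit. The section names three tissue groups (normal, responsive, non-responsive) and no baseline lesional group.

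The visit has to be taken from other sections:

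- Study Summary, Objectives: "utilizing RNA sequencing on responsive and non-responsive tissue at week 4". Section 3, Exploratory Objectives: "identification of unique biomarkers and transcriptomic changes of LP at week 0 and utilizing RNA sequencing on responsive and non-responsive tissue at week 4".
- Section 4.1, on the label: "Responsive and non-responsive lesions will be determined by the change in Modified CAILS between week 0 and 4". Responsive requires a 50% reduction, whereas "non-responsive can have progression, no change, or up to a 50% reduction in Modified CAILS".
- Section 4.1, on week-0 tissue: "up to two 3mm tissue biopsies will be taken from lesional skin and one biopsy will be taken from normal appearing skin". The week-4 biopsies, up to two, are lesional only. The visit lists agree: up to three samples at Day 0 (Section 7.2) and up to two at week 4 (Section 7.6).
- Study Summary, Duration of Administration: "Drug will be administered from Day 0 through Week 8". Section 4.1: "All lesions except for one index lesion will be treated".

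**The concern.** A contrast meant to describe the disease should use diseased tissue that the drug has not touched. Read with the sections above, the tissue called pathogenic in 8.2 is week-4 tissue after four weeks of cream, and its comparator is week-0 normal skin. Disease, drug and visit then differ together. They cannot be separated within the contrast, because no normal skin is sampled at week 4. Half of the pathogenic group may be lesions that by definition have lost at least 50% of their score.

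Two errors follow. A disease gene that the drug normalises is diluted or lost, and a gene changed only by the drug or by time can be listed as a pathogenesis gene. The untreated week-0 lesions, which answer the question directly, are in neither contrast. The choice of test adds a second problem: its first step runs inside one person, on too few samples to select anything.

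**Working it through.** **1. Sample count.** Inputs: 12 subjects (Section 4.2); per subject up to 2 lesional and 1 normal biopsy at week 0, and up to 2 lesional at week 4 (Sections 4.1, 7.2, 7.6). 12 × (2 + 1 + 2) = 60, which reproduces the maximum of 60 in Section 4.1.

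| Tissue | Visit | Maximum | In the 8.2 pathogenesis contrast (week-4 reading) |
|---|---|---|---|
| Normal | 0 | 12 × 1 = 12 | yes |
| Lesional, untreated | 0 | 12 × 2 = 24 | no |
| Lesional, responsive or not | 4 | 12 × 2 = 24 | yes |

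**2. Treatment status at week 4.** Section 4.1 sets aside two index lesions and draws the responsive and non-responsive lesions from the remaining ones. Only one index lesion is left untreated. On the stated design, all of the up to 24 week-4 samples are therefore from treated lesions.

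**3. What each contrast estimates.** Let D be the disease effect on a gene and T the combined effect of drug and elapsed time in a lesion.

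- Week-0 lesional minus week-0 normal = D.
- Week-4 lesional minus week-0 normal = D + T.

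**4. Illustration of both errors.** The assumptions are not in the documents: SD 1, within-subject correlation 0.5, effects in SD units, the mean of two lesional samples per subject, 12 subjects, paired Wilcoxon across subjects at two-sided 5%, one gene, 4,000 simulated trials.

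| Gene | D | T | Flagged, week-0 lesions | Flagged, week-4 lesions |
|---|---|---|---|---|
| Drug or time only | 0 | 1 | 4% | 94% |
| Disease, fully reversed | 1 | −1 | 92% | 4% |
| Disease, half reversed | 1 | −0.5 | 93% | 41% |
| Disease, no drug effect | 1 | 0 | 93% | 93% |

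**5. Link to the protocol's 50% cut.** Assume that a gene's lesion-minus-normal difference moves in proportion to Modified CAILS and that no lesion progresses. A responsive lesion then keeps 0 to 50% of the difference and a non-responsive one 50 to 100%. One of each averages (0 + 50)/2 = 25% to (50 + 100)/2 = 75%. For a paired difference of 1.0 SD at week 0, exact signed-rank power with 12 subjects (one gene, unadjusted 5%, 20,000 simulations) is 0.85. It falls to 0.61, 0.32 and 0.11 when 75%, 50% and 25% is retained.

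**6. The within-subject step.** The smallest two-sided exact rank-sum p is 2 divided by the number of possible arrangements.

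- One normal against two lesional: 2/3 = 0.67.
- One responsive against one non-responsive: 2/2 = 1.0.

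Pairing does not help: one independent pair gives 2/2¹ = 1.0. At any usual threshold, no gene passes to the frequency ranking, and the permutation has nothing to work on.

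**7. Limits of testing across subjects.** The smallest two-sided signed-rank p is 2/2¹² = 0.0005 with 12 pairs, and 2/2⁸ = 0.0078 if only 8 subjects have both tissues. With an assumed 10,000 to 20,000 genes, Bonferroni needs at most 0.05/10,000 = 0.000005, which is out of reach. A 5% false discovery rate needs 0.000488 × 10,000/0.05 = 97.6, so about 98, to 0.000488 × 20,000/0.05 = 195.2, so about 196, genes at that floor together.

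**The case against.** The strongest reply is that 8.2 does not actually say week 4. The combined label could mean all lesional tissue whatever its response, or week-0 biopsies could be labelled afterwards by how their lesion responded. Section 3 places LP biomarkers at week 0, and Section 4.1 has the initial lesional and control biopsies annotated. This keeps another intention possible, so the point is stated as the natural reading. But no text says that week-0 biopsies will be labelled by later outcome, and every statement that gives a visit for responsive and non-responsive tissue gives week 4. Pooling all lesional tissue would still mix in treated lesions, and one normal against four lesional samples within a subject still cannot go below 2/5 = 0.4. Either way 8.2 must state the visit.

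Section 4.1 also mentions photographs of diseased and normal tissue at weeks 0 and 4. That does not add a week-4 normal biopsy: the schedule has five biopsies, three at Day 0 and two lesional at week 4.

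A reader might infer from the within-subject test that no inference across subjects is planned. That is not so, since ranking across 12 subjects and a permutation p value follow. They do not rescue the procedure, because the first step gives them no genes.

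A reader might also infer that the week-0 lesional samples are wasted. The documents do not support this. All samples are to be sequenced, and these may enter the clustering, the principal component analysis and the treated-versus-untreated analysis of Section 4.1. That analysis concerns drug effect, however, is not specified in 8.2, and does not say which samples it means.

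Finally, the work is exploratory, Section 8.2 describes the study as being for estimation only, and the better contrast could be run later on the same data. This limits the weight of the point. It does not justify leaving a biased contrast as the specified one.

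**Conclusion.** The point holds on the natural reading of 8.2 and should be corrected before the sequencing data are analysed. The specified pathogenesis contrast estimates disease plus drug and time. It uses 12 normal and up to 24 treated week-4 samples and none of the up to 24 untreated lesional samples. Its within-subject first step has a floor of 0.67.

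The sample counts and p-value floors follow from the documents. The percentages in steps 4 and 5 are illustrations under assumed effect sizes; they describe a one-gene test across subjects, not the procedure in 8.2, and should not be quoted as the trial's power.

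It would be wrong to infer that the efficacy results are compromised: the primary and secondary endpoints do not use these data. Nor is the week-4 responsive versus non-responsive contrast misconceived. It is a proper pharmacodynamic question, but by itself it cannot identify baseline predictors, although Section 8.1 offers predictive biomarkers as part of the case for a 12-subject design.

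**What to change.** State the visit and the unit of testing for each contrast in Section 8.2:

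1. **Pathogenesis.** Week-0 lesional against week-0 normal skin, paired by subject and tested across the up to 12 subjects, for example on each subject's mean lesional value. Any permutation is done across subjects.
2. **Pharmacodynamics.** Keep week-4 responsive against non-responsive, also tested across subjects. State which samples the treated-versus-untreated analysis in Section 4.1 means. Report any week-4 against week-0 lesional change as drug plus time, not as pathogenesis.
3. **Prediction.** Correlate week-0 lesional expression with all the responses already named in Section 3: Modified CAILS, PGA, BSA and lesion count.
4. **Survival.** Delete the reference to predicting survival, which has no endpoint in this trial.

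No new biopsies or sequencing are needed. The cost is a re-specified analysis and an open limit: given the p-value floor with 12 pairs, gene lists should be reported as effect estimates for follow-up, not as confirmed findings.
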